On a household level, the inclusion criteria (for trial enrolment) will be

1. Location within a cluster that is included in the study
2. Verbal consent from a head of household or an adult authorized by her / him

On a child level, the criteria for receiving study medication will be:

1. Residence in a household enrolled in the trial
2. Age between 29 and 364 days

3. Verbal consent from at least one caregiver

On a child level, the exclusion criteria (for not receiving study medication) will be:

1. Weight below 3.0 kg (3rd centile for healthy 1 month old infants in the WHO growth charts)
2. Known allergy to macrolides, as judged by a caregiver report of the infant experiencing an adverse reaction after oral ingestion of medication, that was deemed likely to be a macrolide by the interviewing data collector.

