We will test the first three of the above-described hypotheses (about malaria elimination and reduction of general or intestinal inflammation) from the first group of children, i.e., 4–11-month-old infants living in communities receiving their 4th MDA. From these infants, a study nurse will collect a heel-prick blood sample and a flocculated rectal swab before they have received any MDA. They will collect another heel prick blood sample and a stool sample (or rectal swab if stool collection fails) two weeks after the 4th round of MDA has been conducted in their communities. From the collected blood, the nurse will measure hemoglobin and CRP concentration with an on-site reader and store blood on a filter paper for later malaria diagnostics with DNA-amplification. From the stool sample, a laboratory technician will determine calprotectin and alpha-1-antitrypsin concentrations with commercially available ELISA tests. Additional stool and urine samples will be collected and stored for later analyses (on hypotheses 5-7). In the analysis phase, we will compare prevalence of malaria parasitemia, mean blood hemoglobin and CRP concentration and mean fecal neopterin, myeloperoxidase, and alpha-1-antitrypsin concentration in the three study arms, both before and after the first MDA treatment.

From the second and third group of children (12–14-month-olds who have received 3-4 doses of MDA and 6–8-month-olds who have received 2-3 doses of MDA) we will test hypotheses 2-4, i.e., those about broader general and intestinal inflammation and immune function and development. These infants will be invited to a health facility or a central location in a village - after the MDA visit to their household. At the clinic, a study nurse will receive a home collected stool sample or take a rectal swab if stool collection has failed. S/he will also draw a 5 ml blood sample and collect a 10 ml

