urine sample, which will be delivered to a nearby study laboratory by a motorcycle messenger. A laboratory technician will measure Hb, separate plasma and white blood cells, aliquot plasma, urine and stool, and store the samples at -80°C freezer. Approximately once a month, the stored samples will be shipped to a central laboratory at CVD-Mali in Bamako, where another laboratory technician will perform the immunological and inflammatory assays. In the analysis phase, we will compare mean plasma concentrations of vaccine antibodies and selected cytokines, thymic output, the ratio of naïve to memory CD4 and CD8 sub-populations in the three study arms. For the azi-biannual group, we will perform an additional exploratory analysis to assess the impact of timing of the azithromycin dose (given at 1-2 and 6-8 months of age vs at 3-5 and 9-11 months of age).

For hypothesis on microbial clearance and reduction of inflammation, we expect to see the largest effect in infants who have not received azithromycin earlier. We also expect that age of the child may be an effect modifier. Hence, we primarily focus on one time-point (fourth MDA) and a wide age-bracket (4–11-month-old infants). The youngest infants (less than 4 months old) will be excluded for logistical reasons as they will not be invited to sample collection for AMR analyses. Since we want to be able to track individual level changes in test variables, we will collect and analyse samples before and after the MDA. The chosen blood analyses can be completed a battery-operated on-site reader from a small volume taken with a heel-prick – and hence we will not need to take any venous samples from these children.

For the hypotheses on immune function and development, we expect to see the largest effect among infants who have received repeated MDA doses. Therefore, we will choose children at a time when there have been at least 4 rounds of MDA in their home villages. At this point, most or all the 12–14-month-old children have received 3-4 MDA doses and 6–8-month-old children have received 2-3 doses. For the immune function and maturity analyses, we will need a larger blood volume and hence we will take it by a venous puncture, at a study clinic after MDA. Since we are interested in a cumulative effect of multiple MDA doses and only want to do group level comparisons, there is no need for paired sample collection.

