The age groups have been selected in a way that there will be no more than one venous blood sample per child during the study. From the 6-8-month of children, we will primarily assess immune development and vaccine responses to tetanus and rotaviral vaccines (given before the age of 6 months). From the 12-14-month of children, we will assess immune development and vaccine response to measles vaccine (given usually between 9 and 12 months of age). From both age-groups, we will also assess malaria prevalence by a DNA amplification test. Immune development and infection are best studied among over-6-month-old children, since by this age infants will have lost most of their passive maternal immunity and will be increasingly susceptible for infection, inflammation, dysbiosis, and EED.

Figure 7 summarises analyses planned to be completed in the first phase.

Study question	Biological specimen	Laboratory analysis	Child age	Level of analysis	Timing of lab sample vs MDA	# of given MDA doses	# of children
Malaria clearance	Blood (dried)	P. falciparum DNA amplification	4-11 mo	Individual	Paired (before and 14 d after)	1	1000
Consequence of malaria clearance	Blood (fresh)	Hemoglobin concentration	4-11 mo	Individual	Paired (before and 14 d after)	1	1000
Reduction of systemic inflammation	Blood (fresh)	CRP concentration	4-11 mo	Individual	Paired (before and 14 d after)	1	1000
Reduction of intestinal inflammation	Stool	Calprotectin concentration	4-11 mo	Individual	Paired (before and 14 d after)	1	1000

Figure 8 summarises biological samples planned to be stored from the study participants (in addition to those, stored in the AMR part of the study). These samples will be used address hypotheses 5-7 of the mechanistic studies as well as for any additional hypotheses formulated during the trial. If all samples were collected and aliquoted as planned, there would be a total of 51,800 stored vials, i.e., these samples will fill one -80°C freezer.

Biological specimen	Child age	MDA or study visit	Timing of lab sample vs MDA	# of given MDA doses	Storage media	Estimated # of aliquots	Volume / aliquot	Storage temperature	# of children
Blood	4-11 mo	4	Before	1-3	Filter paper	2	50 ul	-80°	1000
Stool	4-11 mo	4	Before	1-3	Cryovial	4	1.5 g	-80°	1000
Urine	4-11 mo	4	Before	1-3	Cryovial	3	1.5 ml	-80°	1000
Blood	4-11 mo	4	14 d after	1-3	Filter paper	2	50 ul	-80°	1000
Stool	4-11 mo	4	14 d after	1-3	Cryovial	4	1.5 g	-80°	1000
Urine	4-11 mo	4	14 d after	1-3	Cryovial	3	1.5 ml	-80°	1000

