For growth analysis, we will calculate anthropometric indices LAZ (length for age Z-score), WAZ (weight for age Z-score), WLZ (weight for length Z-score), and MUAC-Z (mid upper arm Z-score) for each participant as described in chapter 4.10. We will then calculate mean (SD) group values for each variable. In analyzing differences between groups, controlling for multiplicity will be conducted as per the closed-testing procedure,

by testing a global null hypothesis at 5% significance level. If the global null hypothesis is rejected ($p<0.05$), three pairwise comparisons will be carried out. The differences between the three groups and their 95% CIs will be obtained from mixed-effects regression models, that account for the clustering of observations. The global p-value will also be obtained from these models.

For mechanism of action analyses, we will calculate the prevalence of malaria parasitemia as well as mean plasma CRP, blood hemoglobin and other biomarker concentration before and at two weeks after the MDA. We will then test a global hypothesis about differences between the groups using mixed-effects models, which account for clustering, for continuous variables and proportions, respectively with different, suitable link functions. If the global test shows a statistically significant difference ($p<0.05$) between the three groups, we will proceed into three pair-wise comparisons, providing the difference (95% CI) in means or proportions. If the p-value obtained from mixed-effects models is <0.05 , the results will be considered supportive of the trial hypothesis.

All children will be analysed in the group into which they were initially randomized, i.e. on an intention-to-treat basis.

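### The mechanism sub-study justifies sampling at the fourth MDA by azithromycin-naive infants, but all resident 4–11-month-olds were age-eligible one round earlier, and 5.02 does not say which contrast tests hypotheses 12–14

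*Combined protocol and SAP*

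**What the plan says.** Section 4.17 bases the timing of the first mechanistic group on this expectation: "For hypothesis on microbial clearance and reduction of inflammation, we expect to see the largest effect in infants who have not received azithromycin earlier". It adds that age may modify the effect, and from these two remarks concludes that the fourth MDA and the 4–11-month bracket are the main focus. Only the first remark bears on which round to use.

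The same section describes the samples in several ways:

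- Under hypothesis 1, the pair surrounds the fourth treatment.
- In the data-collection text, the first blood and rectal samples precede any MDA, and arms are compared "both before and after the first MDA treatment".
- Figure 7 marks the analyses as individual-level and paired, with 1 dose given.
- Figure 8 lists 1–3 doses for the same children at MDA 4.
- The reason given for pairing is: "Since we want to be able to track individual level changes in test variables, we will collect and analyse samples before and after the MDA".

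Section 5.02 will calculate parasitaemia prevalence and "mean plasma CRP, blood hemoglobin and other biomarker concentration before and at two weeks after the MDA", then run a three-group global test with mixed models followed by pairwise differences. It does not say whether the tested quantity is the 14-day value, the pre-dose value or the change. Section 5.01 allows the two azithromycin groups to be combined for hypotheses 12–14.

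**The concern.** The plan claims a property, infants not yet exposed to azithromycin, that the chosen round and age bracket do not have. The pre-dose sample then cannot serve as an untreated baseline in the azithromycin arms.

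What is at stake is what hypotheses 12–14 show. Three quantities could be reported: the effect of the regimen up to day 14 after round 4, the carry-over present just before round 4, and the increment from one more dose. They coincide with a first-dose effect only in unexposed infants. If the text still speaks of a first dose, a null paired result could be read as no antimalarial or anti-inflammatory effect, when it would show only that one further dose added little.

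**Working it through.** **Inputs.** Drug eligibility: "Age between 29 and 364 days" (4.05). Rounds three months apart (4.06). Sampled ages 4–11 completed months at round 4 (4.17). Azi-biannual gets azithromycin in January–June and placebo in July–December (4.06). Coverage: 34 of 39 infants per round found and given MDA (5.04). Conventions assumed here: one month = 30.4375 days, three months = 91.3 days, ages spread evenly over 121.75–365.25 days (243.5 days wide).

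**Reproducing Figure 8's 1–3 doses.** Exactly 4 months at round 4: 121.75 − 91.3 = 30.4 days at round 3, above 29. Just under 12 months: about 364 − 91 = 273 days, below 364. So no resident in the bracket was outside the age window at round 3. The margin for the youngest is thin: the interval may not exceed 121.75 − 29 = 92.75 days.

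Two earlier eligible rounds need age ≥ 182.6 + 29 = 211.6 days; three need age ≥ 273.9 + 29 = 302.9 days.

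| Earlier eligible rounds | Age at round 4 (days) | Share |
|---|---|---|
| 0 | none | 0% |
| 1 | 121.75–211.6 | 89.9/243.5 = 36.9% |
| 2 | 211.6–302.9 | 91.3/243.5 = 37.5% |
| 3 | 302.9–365.25 | 62.3/243.5 = 25.6% |

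The range 1–3 agrees with Figure 8. Section 4.14 likewise describes 4–14-month-olds as children eligible at an earlier round.

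**From eligible to treated, azi-quarterly arm.** Miss rate m = 5/39 = 0.128. If misses are independent between rounds, the untreated share is 0.369m + 0.375m² + 0.256m³ = 0.0473 + 0.0062 + 0.0005 = 5.4%. If the same infants are always missed, it is 12.8%. So about 87–95% had been dosed before the pre-dose sample.

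**Azi-biannual arm, by quarter of round 4.**

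| Round 4 in | Given at round 4 | Rounds 3, 2, 1 | Earlier age-eligible for azithromycin |
|---|---|---|---|
| Jan–Mar | azithromycin | P, P, A | 26% (three earlier rounds) |
| Apr–Jun | azithromycin | A, P, P | 100% |
| Jul–Sep | placebo | A, A, P | 100% |
| Oct–Dec | placebo | P, A, A | 37.5 + 25.6 = 63% |

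Control infants had placebo throughout.

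**What each contrast estimates.** Let e₁ be the azithromycin-minus-control difference just before round 4 and e₂ the difference at day 14. The unadjusted 14-day comparison estimates e₂. A change score estimates e₂ − e₁. Adjustment for the pre-dose value with slope b estimates e₂ − b·e₁. These agree if e₁ = 0. If e₁ has the sign of e₂ and b is positive, the last two are closer to zero than e₂, provided that they do not change sign.

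**Side check.** The detectable difference (1.96 + 0.84)·√(2·DE/n), with n = 333–450 per arm and design effect (DE) 1.6–2, is 0.24–0.31 SD, against 0.25–0.30 stated in 5.04. The sample-size arithmetic is not the problem.

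**The case against.** **The plan does not commit to a change score.** Sections 4.17 and 5.02 describe between-arm comparisons of levels and mention neither subtraction nor baseline adjustment. This stands. A reader might infer that hypotheses 12–14 will be estimated as change from a treated baseline and so be biased towards zero. The documents do not support that: only Figure 7's labels and the sentence about individual changes point that way. What remains is that 5.02 names no tested contrast.

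**The size of any attenuation is unsupported.** A reader might infer a marked loss of power. If a fraction f of the effect persisted to the pre-dose sample, power from a nominal 80% would be Φ(2.80(1 − f) − 1.96), or 56% at f = 0.25 and 29% at f = 0.5. But f has no source in the documents, and the formula assumes the same standard error for a paired contrast. Sections 3.03 and 5.04 report a mortality benefit concentrated in the first three months after a dose, which gives no support to large carry-over, though it concerns mortality and not these markers. Section 4.17, for its part, raises possible carry-over for malaria and cites year-long antibiotic effects on adult microbiota.

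**Some wording has innocent readings.** Figure 8 shows 1–3 doses both before and 14 days after, so it is not a strict count of earlier doses. Figure 7's 1 may be the dose between the paired samples. Section 4.16 uses similar before-any-MDA wording for sampling that precedes dosing at a visit. These readings are fair, but they do not rescue the first-MDA wording or the naive-infant rationale.

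**Eligible is not treated.** Absence, in-migration, weight below 3.0 kg or refusal leave some infants undosed. The 5–13% above reflects planned coverage only.

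**The paired change answers a question the plan asks.** Hypotheses 12–14 do not mention naive infants, and 4.17 wants to know what one dose does in an individual. This stands, and is why the paired change should be kept.

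**Conclusion.** The point holds as an internal contradiction and an unnamed test, not as a demonstrated bias. By age alone, no resident 4–11-month-old at round 4 had missed every earlier round. The 37/38/26% split rests on even ages and exact three-month intervals, and the 87–95% on 5.04's coverage figure. In the azi-biannual arm, prior exposure runs from 26% to 100% by quarter. In half the year its round 4 is placebo, so pooling under 5.01 would mix active drug and placebo at the paired dose. How far a paired or adjusted contrast would understate e₂ is unknown. The mortality outcome is unaffected. The repair is worth making because, as written, the results of hypotheses 12–14 would carry the wrong label.

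**What to change.** 1. Reconcile the passages in 4.17 (hypothesis 1, the data-collection text, the rationale, Figures 7 and 8) so that, with sampling at round 4, none describes a first dose or naive infants. State in both figures whether the dose column counts earlier doses or includes the current one.
2. In 5.02, name the between-arm comparison of 14-day values, not adjusted for the pre-round-4 value, as the test of hypotheses 12–14, and call it the effect of the regimen to date.
3. Report the pre-round-4 between-arm contrast as carry-over, and keep the paired change as a separately labelled estimate of one additional dose.
4. For the 14-day effect, do not pool the azi-biannual arm with the azi-quarterly arm where its round 4 fell in July–December. Record the calendar quarter of round 4 for each village.
5. Optional and exploratory: azi-biannual versus control where round 4 falls in January–March, ages 4–9 months, the closest available to a naive group. It may be empty, since the villages' dates are not given and 4.08 places the tertiary mechanistic sampling in the rainy season.

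The cost is wording and one named analysis on the same samples, some loss of precision from not adjusting for the pre-dose value, and a smaller pooled azithromycin group.

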4.18. Stakeholder perspectives on feasibility, including economic analyses

As previously stated in this protocol (p. 11), in the case of positive clinical results from the LAKANA trial, there is an intention (although not necessarily yet a political commitment) to implement a routine national public health intervention for azithromycin

[figure not shown]
administration in Mali. By studying demand and supply side determinants, the feasibility sub-study aims at providing comprehensive policy advice to the decision makers on if and how this intervention could be implemented, what can be the bottlenecks and how to go around them.

The feasibility study draws from data collected during the main LAKANA clinical trial, but it will also collect data which is not directly linked to the clinical trial MDA approach in order to explore delivery options which are beyond implementation of the current clinical trial protocol. Going beyond the clinical trial protocol is a necessity as any routine public health intervention model would not have the same type of research component as a clinical trial.

The feasibility study framework breaks down to four research components:

1. Acceptability
2. Equity
3. Health system compatibility
4. Economic analysis based on costing and cost-effectiveness analysis

Figure 9 below depicts framework for the feasibility study and its components.

Acceptability

Understanding perspectives and views of various stakeholders on the current LAKANA MDA intervention will form the basis of the acceptability study component. The aim of the acceptability study is to describe how stakeholders conceptualize, perceive and experience the current LAKANA MDA intervention and how they might conceptualize and perceive a future national routine intervention.

Acceptability is a multi-faceted construct that reflects the extent to which stakeholders consider an Azithromycin intervention to be appropriate, based on anticipated or experienced cognitive and emotional responses to the intervention (Sekhon et al 2017). We will confine the present study on health system and household levels (those delivering and receiving the intervention) because of the important role they play. We will focus on local practices and interpretations related to child health, illnesses and well-being and will provide a mostly qualitative analysis of the acceptability of the drug and

the delivery model.

The acceptability study stream will rely on a mixed methods approach: for collecting qualitative data, we will conduct focus-group discussions and semi-structured interviews with families, health workers, *relais*, village chiefs and elders and other key stakeholder groups. Interviews will take place during the trial implementation. Additionally, throughout the intervention, we will conduct in-depth interviews with other stakeholders such as health sector decision makers and politicians. The number of qualitative interviews needed will be based on data saturation. Typically, the total number would be around 50 interviews. We will contextualize the qualitative data using quantitative data collected from all participating households (household socio-economic status, location of residence, family composition and other background variables). We will also collect quantitative data from households through a questionnaire which will be administered in the 59 sub-study villages. The questionnaires will cover questions related to acceptability but also to the economic analysis (see below)

The CVD social science team in collaboration with Point Sud research unit will conduct qualitative interviews in the vernacular (Bambara), transcribed and translated into French. The CVD social science team, together with Tampere University feasibility team will read the interviews immediately after they have been conducted and add new themes to cover topics that remain unanswered to the interview guide. The analysis of the qualitative data will be done using a multipronged approach including thematic and discourse analysis. The analysis might include use of a software such as Atlas.ti. We will analyse quantitative data for proportions and means using Stata software.

Equity

The drugs will be distributed in a research context aiming to determine efficacy of azithromycin. By collecting various types of background information from the study participants and assessing if the background variables (such as poverty or household location), we will be able to assess the equity of impact of this intervention. However, since there will be no data on those whom the study team does not reach, villages that refuse participation, or areas that are excluded from the study due to security or other issues, we will not be able to quantitatively measure equity of access to the intervention. Instead, we will assess equity of access indirectly, using qualitative interviews among stakeholder groups. We will use snowball sampling for selecting the interviewees, but preliminary, we plan to include representatives of multilateral organizations, funding partners, national Ministry of Health (MOH) teams, district MOH teams, volunteer rural health workers, and community members participating in MDA campaigns. In this sub-study, we aim to explore the possible bottlenecks of achieving effective coverage and ways to overcome the difficulties in implementation.

We will consider the village location and accessibility as an equital aspect: we will treat the village's *Strategie Avancée* status as a potential effect modifier of azithromycin MDA. Additionally, we will conduct a survey amongst the field workers to obtain a subjective assessment on how difficult the villages are to reach as a health worker. The results will be assessed in the context of whether the district or health area has a system in place to take the remote and difficult locations into account in terms of arranging health care.

Health system compatibility

The health system compatibility study component aims at answering the study question of: what are the health system compatibility parameters for different implementation scenarios for an Azithromycin public health intervention in the context of Mali?

This study stream will include questions on the transferability of the LAKANA intervention to a scaled-up national intervention, but it will go beyond the LAKANA trial implementation by exploring other possible implementation models. The different possible implementation models are assessed through supply side elements (health system building blocks) in the Malian context. The implementation models will detail the people and institutions involved in each model and the process of implementation of each model.

The health system compatibility study stream will be based on literature and observations on the Malian health system and on interviews with key stakeholders, such as health system researchers, health policy makers, health workers at different levels of the system. The health system compatibility study stream will also draw from lessons learned in implementing the LAKANA trial.

The theoretical framework for the health system compatibility study stream relies on implementation research / science. Bauer et al (2015) have defined implementation science as “The study of methods to promote the adoption and integration of evidence-based practices, policies, research findings and evidence into healthcare policy and practice.”

Economic analysis based on costing and cost-effectiveness analysis

The economic analysis study component aims at answering the study question of: what is the cost of the different implementation models and what are the differences in cost-effectiveness between the different models? The costing exercise will be based on an ingredients approach in which all the different inputs or ingredients that are needed to produce one unit of the intervention need to be costed through market prices or prices derived from competitive market prices. All the prices will be translated into one single monetary unit.

The costs included in the costing are direct, indirect and opportunity costs. The direct costs will be mostly derived and modelled from the LAKANA trial costs with the deduction of research costs. These costs will be modelled to represent the base line MDA approach. For the other implementation models the costing model will require further adjustments according to how the models will be defined. This adjustment can only be done after the implementation models have been developed.

The costing exercise will also include household level opportunity cost. This equates to the indirect cost paid by the participants, more precisely the care givers bringing their children to receive the Azithromycin intervention. To calculate the household level cost the intervention logic (as described above) will need to cover also the household perspective, i.e., what is required from the household (in terms of time and indirect payments to reach the point of service) to receive the service.

The effectiveness will be determined by the trial outcome – both the primary outcome of mortality and the secondary outcomes of morbidity and possible AMR effects. The effectiveness can be expressed in different units such as deaths averted, or disability adjusted life years (DALYs).

Theoretical framework for the costing and cost-effectiveness analysis are based on standard economic evaluation methods – with focus on theoretical frameworks covering economic evaluation of public health programmes (WHO 2004; NICE International, 2014; Sohn et al., 2020).

